The primary purpose of this protocol amendment (03) is to increase the maximum dose in the SAD part of the study from 200 mg to ≤ 700 mg, in relation to human exposure to GSK3640254 being approximately 70% lower than predicted based on animal data. Preliminary PK parameters for GSK3640254 following single dose administration of 1, 3, and 10 mg show exposures that were lower along with a longer half-life than predicted based on animal data. The prediction for a 10 mg dose were a mean C_{max} of 197 ng/mL, a mean AUC of 3430 ng.h/mL and a mean half-life of 15 hours. The observed C_{max} was approximately 75% lower, the AUC was approximately 65% lower and the half-life was about 70% longer. Taking into consideration the actual human PK profile of GSK3640254 at 1, 3 and 10 mg, the minimally anticipated efficacious dose (X) has increased from 40 mg to 70 mg with an accumulation upon repeated once daily administration increasing from 50% to approximately 115%. In order to evaluate exposure anticipated at the maximum MAD dose of up to 4X, higher doses up to 9X will need to be evaluated in the SAD. Thus, this amendment is to enable the evaluation of the safety/tolerability and pharmacokinetics of single doses of GSK3640254 at doses ≤ 700 mg in healthy volunteers continuing to participate in Cohorts 1 and 2. Specifically, the

proposed higher doses will be evaluated in Period 4 (Cohort 1, ≤ 400 mg; Cohort 2, ≤ 700 mg). Other, non-major changes, have also been incorporated.

Amendment 04; 17-MAY-2018

The purpose of this protocol amendment (04) is to study a higher dose of 320 mg QD for 14 days in the MAD part of the study (see Cohort 6 in Figure 1). The MAD 320 mg QD dose would explore steady-state C_{max} values greater than those explored in the SAD study (which is not permitted by the current version of the protocol). This dose of 320 mg QD is four times the projected minimum effective dose (~80 mg QD) and is in line with the MAD PK stopping Criteria in the current approved protocol (amendment 03/ 05 December 2017); specifically, the probability of any subject having an AUC > 61.1 $\mu\text{g}/\text{mL}$ is 42% (data through May 9, 2018). A MAD dose of 320 mg QD allows for a thorough evaluation of PK/QT relationship and a greater safety margin in subsequent clinical trials in patients.

The totality of preliminary PK and safety/tolerability data to date shows the MAD 320 mg QD dose is clinically and scientifically reasonable (see Section 3.2.2 for full details). Specifically, GSK3640254 following single dose administration ultimately showed a plateauing of exposure at the 700 mg dose. On Day 14, the mean C_{max} for the MAD 200 mg dose (1841 ng/ml in Cohort 5) approximated that seen in the SAD at 400 and 700 mg doses (1881 and 1761 ng/ml, respectively). Since the current protocol does not permit a dose in the MAD to surpass the C_{max} studied in the SAD, the ViiV/ GSK Dose Escalation Committee opened the Expansion Cohort (currently ongoing) with a 200 mg dose (See Figure 1) at the conclusion of Cohort 5. Briefly, there have been no significant clinical safety/tolerability findings in the SAD or MAD through May 7, 2018. Preliminary ongoing data review show no deaths or SAEs. There have been 4 individual AEs leading to discontinuation. There have been 10 individual AEs related to blinded study medication. Preliminary review of blinded safety data for the: 1) SAD show 17 subjects experienced 60 individual AEs (58 Grade 1; Two Grade 2) and 2) MAD show 23 subjects experienced 79 individual AEs (77 Grade 1; Two Grade 2). The two most frequent AE SOCs have been Nervous System and Gastrointestinal Disorders without a dose/AE relationship. Subjects recruited for the 320 mg QD Cohort will have the same inclusion/exclusion criteria, have the same study and subject stopping criteria, and undergo the same intensive safety evaluation as previously treated subjects in the MAD. Combined, based upon the preliminary safety and PK data gathered to date (see Section 3.2.2 for full details) subjects will be adequately monitored.

Section # and Name	Description of Change	Brief Rationale
Synopsis Section 5.1 Overall Design	Figure 1 changed and MAD Expansion Cohort Dose added	The actual doses for all Cohorts and Periods updated for the SAD and MAD
Section 3.2.2 Preliminary Safety and PK data in Current Study	Preliminary Safety and PK data from SAD and MAD updated/added	The clinical and PK data is needed to justify the rationale for supporting a proposed dose of 320 mg QD in the MAD (Cohort 6)
Section 3.3 Benefit Risk Assessment	Preliminary Safety and PK data from SAD and MAD updated/added	The clinical and PK data is needed to justify the rationale for supporting an unchanged benefit risk assessment for a proposed dose of 320 mg QD in the MAD (Cohort 6)

1. SYNOPSIS

Protocol Title: A Double-Blind (Sponsor Unblinded), Randomized, Placebo-Controlled, Single and Repeated Dose Escalation Study to Investigate the Safety, Tolerability and Pharmacokinetics of GSK3640254 in Healthy Participants

Short Title: GSK3640254 FTIH study in healthy participants

Rationale: The inhibition of maturation and release of human immunodeficiency virus-1 (HIV-1) is a novel target for drug development, distinct from viral protease, reverse transcriptase and integrase. There are no maturation inhibitors (MI) approved for the treatment of HIV infection. GSK3640254 is a MI that displays *in vitro* evidence of low nanomolar potency against multiple HIV-1 Gag polymorphisms and a broad spectrum covering multiple HIV-1 subtypes, supporting compound development. The goal of this study is to gain information on the safety, tolerability, and pharmacokinetic properties of GSK3640254. This study will enable further clinical development of GSK3640254, including a Phase IIA Proof of Concept (PoC) study in HIV-infected patients.

Objectives and Endpoints:

Objective	Endpoint
Primary	

 To investigate the safety and tolerability of GSK3640254 following single and repeated daily administration 	
 GSK3640254 safety parameters: adverse events; post-baseline values and changes over time of clinical laboratory evaluations (haematology, clinical chemistry, urinalysis), vital signs, and ECG parameters from pre-dose values
Secondary	

 To describe the PK of GSK3640254 following single and repeated daily administration To examine dose proportionality following single and repeated doses of GSK3640254 To assess accumulation of GSK3640254 	
 GSK3640254 PK parameters: Part 1 (single dose): AUC(0-24), AUC(0-tlast), AUC(0-inf), Cmax, C24, tmax, tlag, t1/2, Clast, tlast, CL/F. Part 2 (Repeated QD doses for 14 days): Day 1: AUC(0-24), Cmax, C24, tmax, tlag Day 14: AUC(0-τ), Cmax, Cτ, tmax, t1/2, and CL/F GSK3640254 Single dose: AUC (0-inf), Cmax. Repeat dose AUC(0-τ), Cmax, Cτ Accumulation ratios: R AUC(0-τ), R

Objective	Endpoint

 To assess time to steady-state of GSK3640254 	(C _{max}), R (C _τ) 
 Pre-dose concentrations on Day 2 -14 (Part 2)

ECG= Electrocardiogram; AUC(0-24) = Area under the plasma concentration time curve from zero to 24; AUC(0-inf) = Area under the concentration-time curve from time zero (pre-dose) extrapolated to infinite time; C_{max}= Maximum observed concentration; t_{max}= Time of occurrence of C_{max}; t_{1/2}= Apparent terminal phase half-life; CL/F= Apparent oral clearance

[figure not shown]
Overall Design:

This study is a Phase 1, double-blind (sponsor-unblinded), randomized, placebo-controlled, single- and repeat-dose escalation study of GSK3640254 in healthy participants.

A summary of the overall study design, including doses, sample size, and order, is presented in [Figure 1](#); Schedule of Activities (SoA) tables are included in Section 2.

The proposed dosing schedule is designed to investigate single oral doses of GSK3640254 initially in Part 1 and then, at a suitable cross-over point (described below), repeated once-daily oral dosing of GSK3640254 in Part 2. All doses will be administered immediately following a moderate fat meal (approximately 600 calories with approximately 30% of calories from fat), unless otherwise indicated.

Figure 1 Phase 1 Study in Healthy Participants using planned doses of GSK3640254

Note: A=active, P=placebo. The doses shown here were/are being completed. Amendment 04 proposes to evaluate a 320 mg Daily dose in MAD Cohort 6.

Number of Participants:

A total of approximately 72 randomized participants will be targeted for the entire study. Part 1 will randomize approximately 16 participants, 8 participants in each of Cohort 1 and Cohort 2. Part 2 will randomize approximately 56 participants, 8 participants in each of Cohorts 3 to 6 and 24 participants in the Expansion Cohort.

If participants prematurely discontinue the study in the single ascending dose (SAD), they may be replaced at the discretion of the Sponsor in consultation with the investigator. The replacement participants will be assigned to the same treatment sequence, starting where the prior participant prematurely discontinued. Previously administered doses will not be repeated by replacement subjects if dose escalation criteria are met.

If participants prematurely discontinue the study in the MAD, they may be replaced at the discretion of the Sponsor in consultation with the investigator. The replacement participants will be assigned to the same treatment in the same Cohort where the prior participant prematurely discontinued.

Treatment Groups and Duration:**Part 1 (SAD):**

The SAD portion of the study will be conducted in an interlocking fashion with two separate cohorts of eight healthy participants each. Each of these two cohorts will contain up to four escalating doses of GSK3640254; no more than 8 doses will be assessed in Part 1. The interlocking design as shown in the schematic in [Figure 1](#) and the randomization sequence will allow the 8 participants in each Cohort to potentially receive one of the two lowest and one of the two highest doses of GSK3640254. In each escalating dose period, six participants will be randomized to GSK3640254 and two participants will be randomized to placebo. Each participant will receive placebo once.

To conservatively assess safety in the SAD, within each period and Cohort, 2 out of the 8 participants will serve as sentinel participants with one receiving GSK3640254 and the other receiving placebo (PBO or P in study design scheme). These sentinel participants will be followed clinically for 24 hours after dose administration to monitor the emergence of adverse events. Assuring that there are no safety concerns upon 24 hour review of safety data (e.g. vital signs, ECGs, and adverse events) by the Principal Investigator (PI) for the sentinel participants, the remaining 6 participants will subsequently be treated with either GSK3640254 or PBO according to randomization schedules.

Dose escalation in Part 1 will be determined by the ViiV Healthcare (VH)/ GlaxoSmithKline (GSK) study team and the PI based on the double-blind (sponsor-unblinded) safety data and the PK data from the previous dosing period(s). Dose escalation will not exceed approximately 3-fold between doses up to approximately the predicted minimally effective dose (see Section 5.5) and will not exceed 2-fold thereafter. Twenty-four hour post-dose safety and PK data from a minimum of 4 participants

receiving GSK3640254 are required for dose escalation. Dose escalation will be guided by safety as well as the SAD PK stopping criteria.

Continuous ECGs will be recorded on the day before dosing (Day -1), Day 1, and Day 2 for extraction of ECGs paired with PK sampling.

Part 2 (MAD):

Part 2 (MAD) consists of four ascending repeat-dose cohorts (Cohorts 3 to 6), each with 8 participants (active/PBO=6/2) who will receive a once-daily dose of GSK3640254 or PBO for 14 days. The earliest point at which Part 2 of the study will be conducted is once the single dose safety and preliminary PK data for the anticipated minimally effective dose have been evaluated in the SAD (see [Figure 1](#), MAD). Dose escalation in Part 2 will be determined by the VH/GSK study team and the PI based on the double-blind (sponsor-unblinded) safety and PK data (minimally up to 24 h post Day 14 dose) from the previous dosing period(s). Specifically, 14 days of safety and PK data from a minimum of four participants receiving active drug will be required for dose escalation. In this part of the MAD study, continuous ECGs will be recorded on the day before the first dose (Day -1) and Days 1, 2, 14, and 15 for extraction of ECGs paired with PK sampling.

Part 2 also includes an Expansion Cohort to evaluate the rate of gastrointestinal (GI) intolerability in 24 participants (active/PBO =18/6). The expansion cohort was conducted once the evaluation of the safety and PK from Cohorts 3 – 5 were available. The dose chosen was 200 mg (see [Figure 1](#), MAD).

Participants in both parts will have a screening visit within 28 days prior to first dose and a follow-up visit 7-14 days after the last dose. Maximum duration of study participation will be approximately 12 weeks.

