5.2. Number of Participants

A total of approximately 72 healthy participants will be randomized in the trial: SAD (n~16) and MAD (n ~56).

If participants prematurely discontinue the study in the SAD, they may be replaced at the discretion of the Sponsor in consultation with the investigator. The replacement participants will be assigned to the same treatment sequence where the prior participant prematurely discontinued. Previously administered doses will not be repeated by replacement subjects if dose escalation criteria are met.

If participants prematurely discontinue the study in the MAD, they may be replaced at the discretion of the Sponsor in consultation with the investigator. The replacement participants will be assigned to the same treatment in the same Cohort where the prior participant prematurely discontinued.

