7.4. Blinding

This will be a double-blind study with participants and the site staff blinded. The sponsor will be unblinded (meaning those staff may have access to unblinded data). For dose escalation, the VH/GSK study team physicians, statistician, and clinical pharmacokinetic staff will have access to unblinded data and present data at dose escalation meetings in a blinded fashion when interacting with site staff. Other VH/GSK staff will remain blinded unless unblinding becomes necessary. The blind may be broken if, in the opinion of the investigator, it is in the participant's best interest for the investigator to know the study treatment assignment. The VH/GSK study team must be notified before the blind is broken unless identification of the study treatment is required for a medical emergency in which the knowledge of the specific blinded study treatment will affect the immediate management of the participant's condition. In this case, the VH/GSK study team must be notified within 24 hours after breaking the blind. The date and reason that the blind was broken must be recorded in the source documentation and CRF, as applicable.

Participants will be randomized in a 3:1 ratio to receive study treatment (active drug:placebo) within a period or cohort. Investigators will remain blinded to each participant's assigned study treatment throughout the course of the study.

Unblinded monitors and in the event of a Quality Assurance audit, the auditor(s) will be allowed access to un-blinded study treatment records at the site(s) to verify that randomization/dispensing has been done accurately.

A participant will be withdrawn if the participant's treatment code is unblinded by the investigator or treating physician. The primary reason for discontinuation (the event or condition which led to the unblinding) will be recorded in the CRF.

GSK's Global Clinical Safety and Pharmacovigilance (GCSP) staff may unblind the treatment assignment for any participant with an SAE. If the SAE requires that an expedited regulatory report be sent to one or more regulatory agencies, a copy of the report, identifying the participant's treatment assignment, may be sent to investigators in accordance with local regulations and/or GSK policy.

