8. DISCONTINUATION CRITERIA

8.1. Discontinuation of Study Treatment

A participant will be withdrawn from the study at any time:

- At his or her own request
- At the discretion of the Investigator or the Sponsor for safety (including lab abnormalities or intercurrent illness), psychiatric, compliance, or administrative reasons.
- Emergence of any positive (abnormal) response confirmed by the investigator on a clinician (or qualified designee) administered CSSRS during the on-treatment phase (MAD only)
- Any SAE.
- Termination of the study by GSK/VH. Safety data will be reviewed by the Sponsor in-stream by single case and collectively. If a safety concerns arises, a decision about continuation of the study will be made.
- Loss of ability to freely provide consent due to treatment of either a psychiatric or physical (eg, infectious disease) illness
- Unblinding by the PI for any reason
- Repeat non-adherence by the participant with the requirements of the protocol or treatment (as determined by Investigator in consultation with the Medical Monitor)

If the participant withdraws consent for disclosure of future information, the sponsor may retain and continue to use any data collected before such a withdrawal of consent.

If a participant withdraws from the study, he/she may request destruction of any samples taken and not tested, and the investigator must document this in the site study records.

If a participant withdraws from the study, he/she must complete a follow-up visit.

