8.1.4. Clinical criteria for Stopping the Study

The planned dose escalation within study will be stopped (no new enrollments or further administration of study drug) in the event of any one of the following. However, if any of the criteria are met, an optional cohort may be introduced to assess a lower tolerated dose.

- Two participants within the same Period (SAD) or Cohort (MAD) experience an AE of Grade 3 intensity assessed as related to GSK3640254, by the PI

- One participant experiences an AE of Grade 4 intensity assessed as related to GSK3640254, by the PI
- If greater than 25% of participants within the same Period (SAD) or Cohort (MAD) receiving GSK3640254 have a \geq Grade 3 intensity AE or lab abnormality (with the exception of asymptomatic changes in lipid panel) or a \geq Grade 2 intensity rash with concurrent fever, transaminase elevation or eosinophilia.
- There is one Serious Adverse Event (SAE) or death assessed as related to GSK3640254, by the PI.
- 2 participants with confirmed QTcF \geq 500 msec within the same Period (SAD) or Cohort (MAD)
- 2 participants with clinically significant, in the opinion of the PI, arrhythmias within the same Period (SAD) or Cohort (MAD)

Finally, if a sentinel participant receiving GSK3640254 meets any of these clinical stopping criteria (G3 or G4 drug-related AE; a drug-related SAE or death; or a G2 rash with concurrent fever, transaminase elevation or eosinophilia), the rest of the Period (SAD) or Cohort (MAD) will not dose and further dose escalation will not occur (see Section 5.1). Of note, the intensity of AEs will be determined using DAIDS criteria (see Section 12.4 for further details)

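### In the MAD, the replacement for a participant whose code the investigator has broken inherits that participant's treatment, so the investigator can know it before the first dose

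*Protocol*

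**What the plan says.** On replacement, the Protocol Synopsis and Section 5.2 say of participants who stop early that "they may be replaced at the discretion of the Sponsor in consultation with the investigator". In the MAD the newcomer's allocation is fixed: "The replacement participants will be assigned to the same treatment in the same Cohort where the prior participant prematurely discontinued". In the SAD the newcomer inherits a sequence: "The replacement participants will be assigned to the same treatment sequence, starting where the prior participant prematurely discontinued" (Synopsis).

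On unblinding, Section 7.4 lets the investigator open the code when that serves the participant, and adds: "A participant will be withdrawn if the participant's treatment code is unblinded by the investigator or treating physician". Section 8.1 lists the same trigger among the reasons for withdrawal: "Unblinding by the PI for any reason". Section 7.4 also makes a general commitment: "Investigators will remain blinded to each participant's assigned study treatment throughout the course of the study".

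On use of the investigator's judgement, adverse events are a primary endpoint (Section 4), and the investigator grades each event and assigns causality (Appendix 4). Section 8.1.4 stops escalation on several counts that depend on relatedness. One is that two participants in the same period or cohort "experience an AE of Grade 3 intensity assessed as related to GSK3640254, by the PI". Others are a single related Grade 4 event and a single related SAE or death.

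Neither document exempts a code-broken participant from the replacement rule, gives the newcomer a fresh allocation, or hides whose place is being filled.

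**The concern.** Each rule is reasonable alone. A code break serves the care of the participant whose code is opened, and like-for-like replacement keeps the 6:2 split. Together they pass the knowledge gained from one participant to another for whom there was no medical reason to unblind. The newcomer's own code is never opened, so the SAP's listing of subjects whose blind was broken would, going by its title, not show that this person was in effect unblinded.

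At stake is the independence of the grading and causality calls for that person. On known active drug, events would tend to be called related. On known placebo, they would tend to be called unrelated. At the time of Amendment 04, the parts of the study still open to this were the Expansion Cohort, then running, and Cohort 6 at 320 mg.

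**Working it through.** The plan gives no figure on this point to reproduce. The check is to follow the rules in order and then count.

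**1. The chain (MAD).** The investigator opens a code (Section 7.4). Withdrawal is mandatory (Sections 7.4, 8.1). Replacement is allowed after consulting the investigator (Synopsis, Section 5.2). The only stated allocation is the predecessor's treatment. Given that the investigator knows which place is being filled, the newcomer's treatment is known before the first dose.

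**2. What the investigator knows.** Inputs: 6 active and 2 placebo per cohort of 8; 18 and 6 in the Expansion Cohort (Section 5.1).
- Before any break, the chance that a given participant is on active is 6/8 = 75%, or 18/24 = 75%.
- For the replacement, it becomes 100% or 0%.
- For the other seven in a cohort of 8, it moves to (6−1)/(8−1) = 5/7 = 71% if active was revealed, or 6/7 = 86% if placebo was. In the Expansion Cohort it moves to 17/23 = 74% or 18/23 = 78%. These shifts come from the code break itself, not from the replacement rule.

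**3. Share of the safety summaries.** The Safety population keeps everyone dosed (Protocol Section 10.2, SAP Section 4), so the withdrawn person still counts. Assuming that person was dosed and there is one replacement:
- Cohort of 8: 1/(6+1) = 1/7 = 14% of active, or 1/(2+1) = 1/3 = 33% of placebo.
- 200 mg, with Cohort 5 and the Expansion Cohort displayed together (SAP Section 5.1): 1/(6+18+1) = 1/25 = 4%.
- MAD placebo, pooled by part (SAP Section 5.1): 1/(4×2+6+1) = 1/15 = 7%.

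**4. Stopping rules (Section 8.1.4).** A separate rule stops if more than 25% of those receiving active drug in a cohort have a Grade 3 or higher event, whatever the causality.
- Cohort with 6 active: two such participants give 2/6 = 33%, or 2/7 = 29% with a replacement. Both exceed 25%, so two Grade 3 events on active drug stop escalation without any relatedness call.
- Expansion Cohort: 2/18 = 11%, or 2/19 = 11% with a replacement. The 25% rule is not met, so relatedness decides the two-participant count.
- One Grade 3 event on active and one on placebo in a 6-active cohort gives 1/6 = 17%. Relatedness still decides in that mixed case.
- A single Grade 4 event or SAE stops escalation only if the investigator calls it related. For a replacement of known treatment, that one call is the whole trigger.

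**The case against.** **Replacement is discretionary and the sponsor is unblinded, so it can decline.** True, but nothing tells the sponsor to consider unblinding, and the only allocation it is given is the one that discloses treatment. The discretion makes the event less likely; it is not a safeguard.

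**The commitment to remain blinded sits beside an explicit code-break provision.** That provision covers the participant whose code is opened. It does not extend to someone else who enters later.

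**The most likely emergency unblindings end enrolment anyway.** Largely right. An SAE or Grade 4 event that the investigator calls related stops new enrolment and further dosing, apart from an optional lower-dose cohort. For the same reason the second disclosure route is narrow. Under Section 7.4 an expedited SAE report naming the treatment may reach investigators, and any SAE means withdrawal. What remains is mainly an SAE that the sponsor but not the investigator considers related. The Amendment 04 rationale reports no SAEs through 7 May 2018.

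**Other checks exist.** Grading follows the DAIDS table, and escalation is decided jointly with an unblinded sponsor team. Calling an event on known placebo unrelated to the drug is also correct. These points limit the bias but do not remove it from the investigator's own calls, which feed the primary endpoint.

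**Stronger readings a reader might infer.**
- That one call is half of the Grade 3 trigger in every cohort. The 25% rule makes this untrue for two events on active drug in 6-active cohorts.
- That the SAD is equally exposed. A code showing placebo would identify the sequence and make later periods known active; a code showing active would leave the next period uncertain (active in 2 of 3 possible sequences). But Protocol Table 3 already reports all eight SAD doses with N = 6 each, so the SAD part has little practical value.
- That it has already happened, because 17 SAD participants had AEs against about 16 planned places and 4 AEs led to discontinuation. These figures suggest ordinary replacement at most. No code break is documented.

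**Conclusion.** The point holds for the MAD. The stated rules, followed as written, can give the investigator a replacement's treatment before the first dose, contrary to Section 7.4. It is conditional on a code break (or, narrowly, an SAE report naming the treatment) followed by a decision to replace. The documents give no number of code breaks; the event is probably rare.

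When it occurs, the direct effect is confined to one person's intensity and relatedness judgements: about 1 of 7 active or 1 of 3 placebo within a cohort of 8, 1 of 25 at pooled 200 mg, and 1 of 15 in pooled MAD placebo. It can influence a stop that rests on a single related Grade 4 event or SAE. For two Grade 3 events on active drug, it can influence the stop only in the Expansion Cohort.

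This assumes that the withdrawn person was dosed, that there is one replacement, and that the investigator knows whose place is filled. If several people are replaced at once and the matching is hidden, the inference weakens, but the documents do not provide for hiding it. The documents do not support a claim that the safety results as a whole are unblinded or that any stop has been affected. A one-sentence correction is warranted.

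**What to change.** Add to the Synopsis and Section 5.2: where a MAD participant's treatment has become known to site staff, a replacement does not inherit that treatment. Either the participant is not replaced, or the replacement takes the next number from a 3:1 active-to-placebo reserve list held by unblinded staff. All other replacements stay as planned. The wording should say that the treatment is not inherited. It should not say that the newcomer must receive a different one, because in a two-treatment cohort that would be just as revealing. A 3:1 draw returns the investigator's expectation to 3/4 = 75%.

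The cost is one sentence in two places and a short supplementary list, which Clinical Statistics would have to generate now because Section 7.3 has schedules produced before study start. No participants or procedures are added.

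The downside is balance. Without replacement a cohort of 8 ends 5:2 or 6:1. With one reserve draw it may end 5:3 (active lost, placebo drawn) or 7:1 (placebo lost, active drawn), and 7:1 leaves one placebo participant in that cohort. At least five active remain after one such withdrawal, assuming no other losses, which meets the minimum of four for escalation. No change to SAD sequences is proposed: a fresh draw there could break the rule of one placebo period each and the 6:2 split per period.
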